6.1.6 PERMANENT DISCONTINUATION OF CABOZANTINIB DUE TO ADVERSE EVENTS

Cabozantinib administration should be discontinued if at least one of the following drug-related adverse event(s) occurs:

- Subject no longer experiences clinical benefit as determined by the investigator. If study treatment is withdrawn for this reason, the date of this decision is to be recorded and every effort should be made to continue safety evaluations and collection of subsequent treatment information and follow-up information for survival.
- Unacceptable side effects the investigator feels may be due to study treatment, including any subject with a GI or non-GI perforation/fistula
- Any adverse event, laboratory abnormality or intercurrent illness, which, in the judgment of the Investigator, presents a substantial clinical risk to the subject with continuing study medication.
- Any Grade 3 non-skin, drug-related adverse event lasting $>$ 21 days
Exception of grade 3 drug-related AE:
 - Grade 3 drug-related laboratory abnormalities do not require treatment discontinuation except:
- Any drug-related Grade 4 drug-related adverse event or laboratory abnormality, except for the following events which do not require discontinuation:
 - Grade 4 neutropenia $<$ 7 days;

- Grade 4 lymphopenia or leukopenia;
- Grade 4 amylase or lipase abnormalities that are not associated with symptoms or clinical manifestations of pancreatitis;
- Isolated Grade 4 electrolyte imbalances/abnormalities that are not associated with clinical sequelae and are corrected with supplementation/appropriate management within 72 hours of their onset;
- The investigator feels it is not in the best interest of the subject to continue on study
- Participation in another clinical study using an investigational agent or investigational medical device
- Necessity for treatment with non-protocol systemic anticancer therapy
- Receipt of liver-directed local anti-cancer therapy (eg, transarterial tumor embolization or chemoembolization, radiofrequency or microwave ablation, percutaneous ethanol or acetic acid ablation, injection or infusion of drug eluting or radiation-emitting beads, cryoablation, radiation therapy, including stereotactic radiotherapy, or surgery)
- Necessity for withholding study drug for greater than 8 weeks for AEs, unless continuation of treatment is approved by the Principal Investigator
- Refusal of sexually active fertile subjects (excluding subjects who have been sterilized) to use medically accepted methods of contraception
- Pregnancy of a female subject
- Request by the Principal Investigator
- Subject request to discontinue study treatment
- Significant noncompliance with the protocol schedule in the opinion of the investigator or the Principal Investigator
- The Principal Investigator should be notified of all discontinuations of study treatment as soon as possible. If a subject fails to return for the protocol-defined visits, an effort must be made to determine the reason. If the subject cannot be reached by telephone, at a minimum, a registered letter should be sent to the subject (or the subject's legal guardian) requesting contact with the study site.
- For subjects who withdraw or are withdrawn from study treatment, every effort must be made to continue protocol-specified evaluations and procedures through the post-treatment follow-up and extended follow-up visits unless consent to participate in the study is also withdrawn. All subjects will be followed until death, unless consent to do so is specifically withdrawn by the subject or until a decision by the Principal Investigator is made to stop collection of these data.

If the Investigator consider the option of continue with one of the investigations drugs, the decision to continue with one of the drug-study treatments beyond the criteria mentioned in this point of the protocol should be discussed with the Principal Investigator, Medical Monitor and documented in the study records.

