6.1.4 DOSE MODIFICATIONS

6.1.4.1 CABOZANTINIB DOSE MODIFICATIONS

Cabozantinib dose reduction

Toxicities will be graded using the NCI CTC version 5.0 (see Appendix 4). All dose modifications will follow pre-defined dose levels as indicated below.

The modifications of cabozantinib dosage will follow the following pre-defined dose levels:

Table 1: Cabozantinib dose reduction

| | | |
|------------------------------|----------|--|
| Dose level 0 (standard dose) | 60 mg po | 1 tablet of cabozantinib every day |
| Dose level -1 | 40 mg po | 1 tablet of cabozantinib every day |
| Dose level -2 | 20 mg po | 1 tablet of cabozantinib every day |
| Dose level -3 | 20 mg po | 1 tablet of cabozantinib every 2 or 3 days |

If a patient experiences several toxicities and there are conflicting recommendations, the recommended dose adjustment, which reduces the dose to the lowest level, should be used.

If a dose reduction has been performed, intra-subject dose re-escalation can be considered (up to the maximum of 60 mg daily dose) at the discretion of the treating investigator provided that the toxicities has resolved to at least CTC-Grade baseline levels.

Table 2 Dose Modification Criteria

| Toxicity | Criteria Recommended Guidelines for Management |
|---|--|
| Grade 1 AEs | Continue study treatment if AE is tolerated |
| Grade 2 AEs which are intolerable and cannot be adequately managed | At the discretion of the investigator, study treatment should be dose reduced or interrupted. Note: It is recommended that dose interruptions be as brief as possible. |
| Grade 3 (except clinically non-relevant laboratory abnormalities) | Study treatment should be interrupted unless the toxicity can be easily managed with a dose reduction and optimal medical care. |
| Grade 4 AEs (except clinically non-relevant laboratory abnormalities) | Subjects should have their study treatment interrupted immediately. Discontinue study treatment unless the following criteria are met: Subject is deriving clear clinical benefit as determined by the investigator and agreed by the Sponsor. Toxicity can be managed with a dose reduction following recovery to Grade 1 (or baseline) and optimal medical care |

AE, adverse event.

^a Study treatment dose adjustment is only needed if the toxicity was deemed related to study treatment or had an unclear relationship to study treatment.

^b For dose reduction levels, see Table 1.

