9. STATISTICAL METHODS

9.1 END-POINTS

The study will be analyzed using standard statistical methods to estimate rates and 95%CI (for ORR and other binary variables) by means of the Clopper-Pearson exact method, and the Kaplan-Meier method to describe the survival functions and the median and [95%CI]. Indirect comparisons with will conducted with external data by assessing the 95%CI of the study estimates. A Statistical Analysis Plan, which will include all details regarding all analyses, the interim method, the handling of missing data and any plan for the analysis, will be finalized before the initiation of the study recruitment.

Primary Outcome(s)

- Rate of adverse events (AE) with Common Terminology Criteria for Adverse Events (CTCAE)≥3 excluding palmar-plantar erythrodysthesia, rate of AEs, rate of related-AEs and rate of death. Rate of AEs leading to treatment discontinuation.
- Adverse events will be graded following version 5.0 of the CTCAE of the National Cancer Institute, during treatment and 30 days after the last dose.

Secondary Outcome(s)

Time to progression, objective response rate, pattern of progression, overall survival, post-progression survival, rate of patients who develop new extrahepatic spread. Serum and tissue marker characterization.

Safety Outcomes

This is a clinical trial were the main purpose is the assessment of safety, therefore, the primary and secondary outcomes were defined accordingly, as described above.

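### Protocol Table 2 and Section 6.1.6 give conflicting stopping instructions for the same drug-related grade 4 event

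*Protocol*

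**What the plan says.** Table 2 (Protocol 6.1.4.1) has a row for "Grade 4 AEs (except clinically non-relevant laboratory abnormalities", which leaves such laboratory findings outside the rule. For the remaining grade 4 events the instruction is "Subjects should have their study treatment interrupted immediately. Discontinue study treatment unless the following criteria are met". Two criteria follow: "Subject is deriving clear clinical benefit as determined by the investigator and agreed by the Sponsor", and "Toxicity can be managed with a dose reduction following recovery to Grade 1 (or baseline) and optimal medical care". A footnote sets the scope: "Study treatment dose adjustment is only needed if the toxicity was deemed related to study treatment or had an unclear relationship to study treatment".

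Section 6.1.6 has its own grade 4 item: "Any drug-related Grade 4 drug-related adverse event or laboratory abnormality, except for the following events which do not require discontinuation". The events that follow are neutropenia lasting less than 7 days, lymphopenia or leukopenia, amylase or lipase changes without symptoms or clinical signs of pancreatitis, and isolated electrolyte disturbances corrected within 72 hours. The item contains no route based on benefit or dose reduction. The last paragraph of 6.1.6 allows treatment beyond its criteria after a documented discussion with the principal investigator and medical monitor.

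The protocol puts both texts into use. Section 4.1.2 sends sites to 6.1.4.1 for dose reduction and resumption. Section 4.1.4, repeated in SAP 7.3.2, includes the 6.1.6 criteria among the situations in which study medication must be stopped.

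Protocol 9.1 lists "Rate of AEs leading to treatment discontinuation" under the primary outcomes, and Protocol Section 2 and SAP 8.3.1 do likewise. SAP 8.6.5.1 reports it as a rate with an exact Clopper-Pearson 95% interval.

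**The concern.** One event, in one patient, meets two sets of instructions. Neither passage refers to the other on this point or says which takes precedence. A grade 4 laboratory value judged not clinically relevant, but absent from the 6.1.6 list, falls outside the rule in Table 2 and is a reason to stop in 6.1.6. A clinical grade 4 event may continue under Table 2 with the sponsor's agreement. Under 6.1.6 it is a stop unless different people are consulted.

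The first thing at stake is consistent handling of the most severe toxicity across seven sites, including what counts as a protocol deviation. The second is interpretation. If sites follow different passages, the discontinuation rate partly describes the choice of passage and not only the drug's tolerability in this population.

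**Working it through.** The plan states no figure on this point, so the check is a comparison of texts, followed by arithmetic for scale.

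**Step 1. The two rules for a drug-related grade 4 event**

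| Feature | Table 2 (6.1.4.1) | Section 6.1.6 |
|---|---|---|
| Default | Interrupt at once, then stop unless criteria are met | Stop |
| Route to continue | Clear benefit, sponsor agreement, and toxicity manageable by dose reduction after recovery | None in the item; general override at the end of the section |
| Who is involved | Investigator and sponsor | Investigator, principal investigator, medical monitor |
| Laboratory exceptions | Open class, by clinical relevance | Closed list |
| Relatedness | Related or unclear | Drug-related |

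The rows differ in substance. A site that applies Table 2's laboratory exemption needs nobody's approval, so it would never reach the override in 6.1.6.

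**Step 2. Test cases from the protocol's own sections**

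- *ALT, AST or bilirubin.* Section 6.1.4.4 covers patients with baseline values up to 3 times the upper limit of normal who reach grade 3 or higher. It sends them to interruption and dose reduction under Table 2. That range includes grade 4, and these tests are not on the 6.1.6 list. (6.1.4.4 separately requires permanent stopping for the combined transaminase and bilirubin pattern that suggests drug-induced liver injury. The conflict concerns the other elevations.)
- *Thrombocytopenia.* Section 6.1.4.5 allows management by interruption or reduction and names no grade limit. Thrombocytopenia is not on the 6.1.6 list.
- *Lipase.* Section 6.1.5 allows resumption after a grade 4 abnormality that is either asymptomatic or without radiographic findings. Section 6.1.6 exempts only cases without symptoms or clinical signs of pancreatitis. A symptomatic case with clear imaging falls on different sides.

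These toxicities are plausible in this trial. Section 1.2.2 reports, among 41 HCC patients starting at 100 mg, grade 3 or higher thrombocytopenia in 17% and AST increase in 12%. For the phase 3 trial it gives grade 3 AST/ALT increase in 11%. The grade 4 share is not reported.

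**Step 3. Scale**

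With the planned 40 patients, one patient whose stop depends on the passage followed moves the rate by 1/40 = 2.5 points. Two such patients move it by 5 points and four by 10. The documents give no expected discontinuation rate, so the counts below are assumptions. The intervals use the SAP's method:

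- 4/40 = 10.0% (95% CI 2.8 to 23.7)
- 6/40 = 15.0% (5.7 to 29.8)
- 8/40 = 20.0% (9.1 to 35.6)
- 10/40 = 25.0% (12.7 to 41.2)

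A shift of a few patients is well inside the width of any one interval, but it would move the point estimate visibly.

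**Step 4. Reach into the formal decision**

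Protocol 9.2 bases the sample size, the futility rule and the rejection rule on AEs of grade 3 or higher excluding palmar-plantar erythrodysesthesia. A patient with any other grade 4 AE already counts there, whether treatment stops or continues. On a per-patient count, that event cannot change the Simon result.

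**The case against.** The strongest reply is that the two rules are close. Both default to stopping, and both allow continuation after central consultation, so 6.1.6 should not be read as an absolute ban. The cross-references also divide the work in part: 6.1.4.1 for dose changes and 6.1.6 for permanent stopping. This softens the conflict but does not resolve it. Table 2 contains its own discontinuation instruction, the conditions and approvers differ, and the laboratory exemptions do not match. The sentence in 6.1.4.1 that settles conflicting recommendations by the lowest dose concerns a patient with several toxicities, not one toxicity under two stopping rules.

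A reader might infer that the same event could be counted or not counted in the endpoint. The documents do not support that. The synopsis requires the action taken for each AE, including drug withdrawal, to be recorded. SAP 8.6.5.3.7 tabulates action taken and permanent discontinuation, and SAP 8.5 uses all observed data under treatment policy. The endpoint counts stops that happened. What can vary is the decision to stop, and 6.1.6 already leaves part of that to the investigator's judgement, so aligned wording would not make the rate wholly rule-driven.

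It is also fair to say that discontinuation is one of several primary endpoints that SAP 8.5 calls non-confirmatory, in an analysis that SAP 8.6 calls non-inferential. The synopsis list of primary outcomes omits it, although the synopsis objective, Protocol 9.1 and the SAP include it. That limits the weight of the point. It does not remove the contradictory instructions.

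**Conclusion.** The contradiction stands. Table 2 and Section 6.1.6 direct different handling of the same drug-related grade 4 event, and nothing in the documents settles which applies. The practical consequence is inconsistent management of severe toxicity between sites. The statistical consequence is limited: the observed discontinuation rate may partly reflect the passage followed, by 2.5 points per affected patient if 40 are treated.

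The number of affected patients cannot be derived from the documents, so no total effect can be stated. A reader might take the label of primary outcome to mean that the trial's go/no-go result is at risk. It is not, provided critical AEs are counted per patient. This is a point to correct, not a threat to the trial's main conclusion.

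**What to change.** The sponsor should reconcile Table 2, Section 6.1.6 and the related passages (6.1.4.4, 6.1.4.5 and 6.1.5) so that one grade 4 rule, one list of laboratory exceptions and one approval route apply. The passages should refer to each other. Which rule is right is for the sponsor to decide.

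SAP 8.3.1 can stay as it is, because an endpoint built on discontinuations that occurred does not need the stopping rule in its definition. The cost is a protocol wording amendment, with no effect on sample size or analysis.

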6.1.7 STOPPING RULES FOR CLINICAL DETERIORATION

Clinical deterioration will be assessed to have occurred after a clinical event that, in the Investigator's opinion, is attributable to disease progression, is unlikely to reverse with continued study treatment and

therefore indicates that the subject is not benefiting from study treatment and cannot be managed by the addition of supportive care (such as bisphosphonates, bone directed radiotherapy, thoracentesis or paracentesis of accumulating effusions). The decision to continue or stop treatment should be discussed with the Principal Investigator and Medical Monitor as well as will be documented in the study files.

Examples of events that may, in the Investigator's opinion, indicate a lack of clinical benefit include, but are not limited to, the following:

- Performance status decrease of at least 2 points from baseline despite transitory cabozantinib interruption for at least 4 weeks
- Skeletal related events defined by spinal cord or nerve root compression.
- Development of new central nervous system metastases or Grade 3 encephalopathy despite transitory cabozantinib interruption for at least 2 weeks
- Any setting where the initiation of new anti-neoplastic therapy has been deemed beneficial to the patient.

6.1.7.1 TREATMENT WITH CABOZANTINIB BEYOND DISEASE PROGRESSION

In the absence of clinical deterioration, it is thus reasonable that subjects will be allowed to continue study therapy after an initial investigator-assessed RECIST 1.1 defined progression (based on a comparison with baseline or nadir scans or other tumor evaluations) as long as they meet the following criteria:

- Investigator assessed clinical benefit
- Treatment beyond progression will not delay an imminent intervention to prevent serious complications of disease progression (e.g., CNS metastases)
- These criteria aim to ensure the risk/benefit of continuing treatment will continue to favor the subjects due to the current data available about the impact of the pattern of progression on post-progression survival²⁰⁻²⁴. The assessment of clinical benefit should consider whether the subject is clinically deteriorating and unlikely to receive further benefit from continued treatment. The decision to start or continue with the drug-study treatments beyond initial investigator-assessed progression should be discussed with the Principal Investigator, Medical Monitor and documented in the study records. If the decision is taken to continue cabozantinib treatment beyond progression, the subject will remain on the trial and continue to be treated and monitored according to the Time and Events Schedule in [Section 8](#).

6.2 CONCOMITANT TREATMENTS

6.2.1 PERMITTED TREATMENTS

- Standard therapies for concurrent medical conditions. Prophylactic anti emetics may be administered according to standard practice.
- Antiviral treatment for chronic HBV.
- Megestrol acetate (Megace[®]) as supportive care
- Bisphosphonates
- Low dose aspirin for cardioprotection (per local applicable guidelines), low-dose warfarin (≤ 1 mg/day), and low dose LMWH are permitted. The protocol does not restrict the use of heparins

at prophylactic doses. Therapeutic doses of heparins are allowed if clinically indicated for supportive treatment and the benefit outweighs the risk per the investigator's discretion. During treatment with anticoagulants, subjects need to be monitored on an ongoing basis for bleeding risk and signs of bleeding. Therapeutic doses of oral anticoagulants (eg, warfarin or warfarin-related agents, thrombin or FXa inhibitors, antiplatelet agents such as clopidogrel) are not allowed.

6.2.2 PROHIBITED TREATMENTS

- Systemic anticancer therapy including cytotoxic therapy, signal transduction inhibitors, hormonal therapy (unless hormonal replacement therapy was initiated prior the study inclusion) and experimental or approved therapies during this trial or within 30 days before starting to receive study medication, except prior therapy with sorafenib as detailed in the current protocol.
- Any drug that targets angiogenesis, especially VEGF and VEGFR.
- TKIs other than cabozantinib
- Bone marrow transplant or stem cell rescue.
- Patients taking narrow therapeutic index medications (e.g., warfarin, phenytoin, quinidine, carbamazepine, phenobarbital, cyclosporine, and digoxin) should be monitored proactively.
- For anticoagulants and low dose aspirin see 6.2.1 section.

Therapeutic monitoring should be performed consistent with the local clinical standard of care following dose modification of the agent. In general, patients should be closely monitored for side effects of all concomitant medications regardless of path of elimination.

Additional information on potential drug interactions with cabozantinib is provided in Section 14.7

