| Patients with HCC intolerant to sorafenib according to the RESORCE trial definition or those patients who received other first-line treatment. |
| Inclusion Criteria (detailed) |
| 
HCC diagnosed according to criteria of American Association for the Study of Liver Diseases (AASLD) definition in 2010.Intolerant to sorafenib according to RESORCE trial definition or patients who received treatment different to sorafenib as first-Line treatment .The subject has disease that is not amenable to a curative treatment approach (eg, transplant, surgery, radiofrequency ablation)Recovery to ≤ Grade 1 according to (CTCAE) v.5.0. from toxicities related to any prior treatments, unless the adverse events are clinically non-significant and/or stable on supportive therapyRespect the 15 days of first-line treatment washout before starting cabozantinibAge ≥ 18 years old on the day of consentECOG performance status of 0 or 1Adequate hematologic function, based upon meeting the following laboratory criteria within 7 days before starting therapy:
absolute neutrophil count (ANC) ≥ 1200/mm³ (≥ 1.2 x 10⁹/L)platelets ≥ 60,000/mm³ (≥ 60 x 10⁹/L)hemoglobin ≥ 8 g/dL (≥ 80 g/L)Adequate renal function, based upon meeting the following laboratory criteria within 7 days before starting therapy:
Serum creatinine ≤ 1.5 × upper limit of normal or calculated creatinine clearance ≥ 40 mL/min (using the Cockcroft-Gault equation: (140 – age) x weight (kg)/(serum |

| |
|---|

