5. PATIENT POPULATION

For entry into the study, the following criteria MUST be met. Eligibility criteria for this study have been carefully considered to ensure the safety of the study subjects and to ensure that the results of the study can be used.

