5.1.2 TARGET POPULATION

- HCC diagnosed according to criteria of American Association for the Study of Liver Diseases (AASLD) definition in 2010.
- Intolerant to sorafenib according to RESORCE trial definition or patients who received treatment different to sorafenib as first-Line treatment.
- The subject has disease that is not amenable to a curative treatment approach (eg, transplant, surgery, radiofrequency ablation)
- Recovery to \leq Grade 1 according to (CTCAE) v.5.0. from toxicities related to any prior treatments, unless the adverse events are clinically no significant and/or stable on supportive therapy
- Respect the 15 days of first-line treatment washout before starting cabozantinib
- Age \geq 18 years old on the day of consent
- ECOG performance status of 0 or 1
- Adequate hematologic function, based upon meeting the following laboratory criteria within

7 days before starting therapy:

- a. absolute neutrophil count (ANC) $\geq 1200/\text{mm}^3$ ($\geq 1.2 \times 10^9/\text{L}$)
- b. platelets $\geq 60,000/\text{mm}^3$ ($\geq 60 \times 10^9/\text{L}$)
- c. hemoglobin $\geq 8 \text{ g/dL}$ ($\geq 80 \text{ g/L}$)
- Adequate renal function, based upon meeting the following laboratory criteria within 7 days before starting therapy:
 - a. Serum creatinine $\leq 1.5 \times$ upper limit of normal or calculated creatinine clearance $\geq 40 \text{ mL/min}$ (using the Cockroft-Gault equation: $(140 - \text{age}) \times \text{weight (kg)} / (\text{serum Creatinine} \times 72 [\text{mg/dL}])$ for males. (For females multiply by 0.85).

AND

- b. urine protein/creatinine ratio (UPCR) $\leq 1 \text{ mg/mg}$ ($\leq 113.1 \text{ mg/mmol}$) or 24-hour urine protein $< 1\text{g}$
- Child-Pugh Score of A
- Total bilirubin $\leq 2 \text{ mg/dL}$ ($\leq 34.2 \mu\text{mol/L}$) within 7 days before starting therapy
- Serum albumin $\geq 2.8 \text{ g/dL}$ ($\geq 28 \text{ g/L}$) within 7 days before starting therapy
- Alanine aminotransferase (ALT) and aspartate aminotransferase (AST) ≤ 5.0 upper limit of normal (ULN) within 7 days before starting therapy
- Hemoglobin A1c (HbA1c) $\leq 8\%$ within 28 days before starting therapy (if HbA1c results are unavailable [eg, hemoglobin variant], a fasting serum glucose $\leq 160 \text{ mg/dL}$)
- Antiviral therapy per local standard of care if active hepatitis B (HBV) infection
- Capable of understanding and complying with the protocol requirements and signed informed consent

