9.2 SAMPLE SIZE

The sample size calculation will be triggered by the primary outcome, i.e, the rate of adverse events (AE) with CTCAE \geq 3 excluding palmar-plantar erythrodysthesia (critical AEs). The expected rate for this outcome was 56% in this population¹. The Simon's two-stage optimal design² will be used to test the alternative hypothesis that with cabozantinib the rate of critical AEs will be reduced at least to 32.5% against the null hypothesis of 56% as previously observed. In the first stage, 14 patients will be accrued. If there are 8 or more critical AEs in these 14 patients, the study will be stopped because of futility. Otherwise, 26 additional patients will be accrued for a total of 40. The null hypothesis will be rejected if 23 or fewer critical AEs are observed in 40 patients. This design yields a type I error rate of 2.5% one-sided and power of 80% when the true response rate is 67.5%.

All patients exposed to the study treatment (regardless of protocol adherence) will count be safety, and thus no need to sample size increases as per potential withdrawals are foreseen.

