8 STATISTICAL ANALYSIS

8.1 ANALYSIS POPULATIONS

There are only one population for this study:

- Safety Set: All eligible patients who have received at least one dose of Cabozantinib will be included in the Safety population.

The population will be fully defined and documented during the Data Review and before the database lock. The objective will be to carry out the population selection and definition of the final study population.

The Safety population will be used for all analysis including the efficacy secondary endpoints.

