Table 45. End of study.

Table 46. Concomitant medication. Number (%) of subjects reporting one or more concomitant medication (globally and by type ATC code).

Table 47. Adverse events. Summary of number (%) of subjects reporting one or more AE, severe AE, AE (CTCAE)≥3 excluding palmar-plantar erythrodysthesia, treatment-related AE, severe treatment-related AE, AE with death, serious AE, treatment-related serious AE, AE leading to disc., treatment-related AE leading to disc.

Table 48. Adverse events. Number (%) of subjects reporting one or more treatment-emergent adverse events (in general and by System Organ Class).

Table 49. Adverse events. Number (%) of subjects reporting one or more treatment-emergent adverse events and number of AE occurrences by body system and preferred term.

Table 50. Adverse events. Number (%) of subjects reporting one or more treatment-emergent adverse events and number of AE occurrences by seriousness.

Table 51. Adverse events. Number (%) of subjects reporting one or more treatment-emergent adverse events and number of AE occurrences by severity.

Table 52. Adverse events. Number (%) of subjects reporting one or more treatment-emergent adverse events and number of AE occurrences by action taken.

Table 53. Adverse events. Number (%) of subjects reporting one or more treatment-emergent adverse events and number of AE occurrences by causality.

Table 54. Adverse events. Number (%) of subjects reporting one or more treatment-emergent adverse events and number of AE occurrences by outcome.

Table 55. Adverse events. Number (%) of subjects reporting one or more treatment-emergent adverse events and number of AE occurrences by severity, seriousness and causality.

Table 56. Adverse events. Number (%) of subjects reporting one or more treatment-emergent adverse events and number of AE occurrences by NCI CTCAE v5.0.

Table 57. Protocol deviations. Number (%) of subjects reporting one or more protocol deviation.

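### Two washout rules conflict: 15 days for any first-line drug in the inclusion criteria, 30 days for anything but sorafenib in Protocol 6.2.2

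*Protocol*

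**What the plan says.** Protocol 5.1.2 admits patients by either of two routes: sorafenib intolerance on the RESORCE definition, or "patients who received treatment different to sorafenib as first-Line treatment". The same section, the synopsis inclusion list and the 7.1 flow chart all give the washout as "Respect the 15 days of first-line treatment washout before starting cabozantinib". None of the three distinguishes by drug.

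Protocol 6.2.2 lists, among prohibited treatments, "Systemic anticancer therapy including cytotoxic therapy, signal transduction inhibitors, hormonal therapy" and experimental or approved therapies. It applies the bar during the trial and also "within 30 days before starting to receive study medication, except prior therapy with sorafenib as detailed in the current protocol".

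Protocol section 5 introduces its lists with "For entry into the study, the following criteria MUST be met". The 30-day interval is written in neither 5.1 nor 5.2.

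On who is analysed, SAP 8.1 says "All eligible patients who have received at least one dose of Cabozantinib will be included in the Safety population". Protocol 9.2 says "All patients exposed to the study treatment (regardless of protocol adherence) will count be safety", and SAP 7.4 repeats that sentence. The SAP also plans "Table 57. Protocol deviations. Number (%) of subjects reporting one or more protocol deviation".

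**The concern.** The 6.2.2 exception covers prior sorafenib only and leaves out the other branch that the trial was set up to enrol. For that branch the protocol gives two minimum intervals and no order of precedence.

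Three things follow.

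- **Enrolment.** One site can enrol a non-sorafenib patient at day 15 under 5.1.2, while another makes the same patient wait until day 30 under 6.2.2.
- **Deviation counts.** A patient who satisfied the written inclusion criterion may still be recorded as a deviation in SAP Table 57.
- **Subgroups.** SAP 8.7 analyses the primary and secondary endpoints by first-line treatment, sorafenib versus other. Where 6.2.2 is followed, the minimum washout is 15 days in one group and 30 in the other. That is an avoidable difference in a trial whose main endpoint is grade 3 or higher adverse events.

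A related point concerns the analysis set. If a 6.2.2 breach were read as ineligibility, the wording of SAP 8.1 could remove a treated patient from the safety analysis, although Protocol 9.2 and SAP 7.4 would count that patient.

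**Working it through.** The plan states no figure to reproduce on this point. The check compares the two rules and then works a small sensitivity for the Safety Set wording.

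**Step 1: the conflict window.** Let *g* be the number of days from the last dose of first-line treatment to the first dose of cabozantinib. (Counting from the last dose is an assumption; the protocol does not define the start.)

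- 15-day rule (synopsis, 5.1.2, 7.1): met if *g* ≥ 15.
- 30-day rule (6.2.2): breached if *g* < 30, unless the prior drug was sorafenib.

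| Gap *g* | Non-sorafenib: 15-day rule | Non-sorafenib: 6.2.2 | Sorafenib |
|---|---|---|---|
| under 15 | fails | breached | fails the 15-day rule |
| 15 to 29 | met | **breached** | no conflict |
| 30 | met | depends on whether day 30 is included | no conflict |
| over 30 | met | met | no conflict |

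The window holds 29 − 15 + 1 = 15 whole-day values, and it exists only in the non-sorafenib branch.

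**Step 2: does other text settle it?**

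- The section 6.2 heading is about concomitant treatment, but the 6.2.2 bullet explicitly reaches back before the first dose.
- The closing words of the 6.2.2 exception, which point to the rest of the protocol, qualify prior sorafenib. They do not extend to other drugs.
- Protocol 4.1.1 allows at most 28 days from consent to first dose. That sets no minimum, so it does not remove the conflict. It does tighten the timing: a non-sorafenib patient who consents on the day of the last first-line dose must start with *g* ≤ 28, which cannot satisfy a 30-day bar.
- Protocol 3.1 requires strict adherence to everything the protocol specifies, so neither rule can be set aside.

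**Step 3: the Safety Set wording.** Suppose one treated patient of 40 were removed as not eligible. The two counts are illustrative: 23 is the plan's final boundary, and 13 of 40 equals the 32.5% alternative (Protocol 9.2).

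| Starting rate | Removed patient had the event | Removed patient did not |
|---|---|---|
| 23/40 = 57.50% | 22/39 = 56.41% (−1.09 points) | 23/39 = 58.97% (+1.47 points) |
| 13/40 = 32.50% | 12/39 = 30.77% (−1.73 points) | 13/39 = 33.33% (+0.83 points) |

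The shift per patient is small. However, the decision rules are fixed counts (8 or more of 14 at the interim, 23 or fewer of 40 at the end). A disputed patient matters most at a boundary.

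**The case against.** The strongest reply is that the two rules can be applied together. Fifteen days is a minimum, 6.2.2 sets a longer one for non-sorafenib drugs, and a gap above 30 days satisfies both. A cautious site breaches nothing. Protocol 4.1.1 also tells sites to contact the study monitor when eligibility is in doubt. The last exclusion criterion in 5.2.1 bars patients unable to comply with prohibited treatments, which supports reading the rules as cumulative.

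Part of this stands: compliance with both rules is possible, and the query route may reduce variation between sites. It does not resolve the conflict. The query route does not say which rule prevails. Linking prohibited treatments to eligibility makes matters sharper, because a patient can then meet the washout criterion and still be called ineligible.

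A second reply is that the consequence is small and that the Safety Set wording is a separate issue. Both are fair. The percentages in the working measure only the Safety Set point; the washout conflict itself has no quantified effect. The Safety Set point stands on its own, since SAP 8.1 and SAP 7.4 disagree whatever the washout interval.

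A third reply is that the documents justify neither interval, so choosing 15 days is a clinical decision. That is accepted: what is needed is one interval, and the sponsor should choose it.

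**Conclusion.** The inconsistency is real. For non-sorafenib patients with a gap of 15 to 29 days, the inclusion criterion and 6.2.2 give opposite answers and no text ranks them. This rests on counting both intervals from the last first-line dose and on reading the sorafenib exception literally.

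The size is modest. Neither the share of non-sorafenib patients nor the number in the window is given, and the latter could be zero. The effect falls mainly on enrolment practice and deviation counts. The treatment-policy rule in SAP 8.5, with Protocol 9.2 and SAP 7.4, keeps treated patients in the primary analysis. The one opening is the word 'eligible' in SAP 8.1, worth between −1.7 and +1.5 points per excluded patient in the cases worked. No change in the trial's conclusion is shown. The point should be corrected because it is clear-cut and touches one of the two target groups.

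**What to change.** State one washout interval throughout the protocol. Either of these does it:

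- Change the 6.2.2 exception to: *except prior first-line therapy that meets the washout in Section 5.1.2*.
- If 30 days is wanted for drugs other than sorafenib, write that into the synopsis, 5.1.2 and 7.1, and say whether day 30 itself is allowed.

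Separately, delete 'eligible' from the Safety Set definition in SAP 8.1 so that it matches Protocol 9.2 and SAP 7.4.

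The text change is one phrase in the protocol (or three short insertions under the second option) and one word in the SAP, with no added patients, visits or procedures. A protocol edit still needs ethics approval (10.1) and signature by each centre's principal investigator (section 10), across 7 planned sites. Version 4.0 is dated July 2021 and enrolment was planned to end in July 2022, so an amendment helps only patients enrolled after it. If enrolment has closed, a written rule before database lock on how to classify gaps of 15 to 29 days, together with the SAP edit, is enough.
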